Ketamine has a rapid onset and relatively short duration when administered as a single intravenous dose. Onset of action for intravenous dose is 30 seconds; distribution half-life 10 minutes; elimination half-life 2-3 hours. Oral bioavailability is poor (20-25%) possibly due to the hepatic first pass effect/GI tract effect. Ketamine undergoes rapid demethylation to norketamine via cytochrome P450 (CYP) conversion, with CYP3A4 being the principle pathway, with minor and clinically insignificant contributions from CYP2B6 and CYP2C9.⁵⁰ Bioavailability of intranasal ketamine was found to be 50% in children aged 2-9 year old in a study done by Malinkovsky et al. in 1996². However this study was done in children and the subjects did not serve as their own controls. In a study by Yanagihara et al. in 2002 the bioavailability of intranasal ketamine was found to be 45%. In this study the subjects served as their own controls, however, the number of subjects was limited to 3. The time for maximum concentration after *intranasal* ketamine administration was found to be 22.5(+ 9.6) min for ketamine and 120(+ 52) min for its metabolite norketamine. The $T_{1/2}$ _{β} (elimination half-life) of *IV* ketamine is reported to be 126.8(+47.4) min by Yanagihara et al²³. Elimination half-life of intranasal ketamine has not been reported. Ketamine has high lipid solubility and crosses the blood-brain barrier quickly, and exhibits high hepatic clearance and a large volume of distribution. It undergoes extensive hepatic metabolism by the cytochrome P-450 system to form the

active metabolite, norketamine. Norketamine is one-third to one-fifth as potent as Ketamine. Norketamine is eventually conjugated to form more inactive metabolites that are excreted by the kidneys.

A3. Preliminary Data:

To date, we have collected data on two cases of cancer patients to whom ketamine was delivered palliatively for pain unresponsive to usual interventions:

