Intranasal ketamine will be prepared from a 100 mg/mL vial to be delivered nasally with a nasal atomizer. We will deliver 0.1 ml to provide 10 mg of atomized ketamine. Alternating nares will be used to deliver 0.1 ml at a time until the full dose is delivered. In the intranasal ketamine study for breakthrough pain by Carr et al., 10 to 50 mg of intranasal ketamine was given regardless of the patient's weight. IV ketamine analgesic doses are >100 ng/ml²⁴. Lapidus et al. found the mean ketamine plasma concentration to be 72 ng/mL at 20 min and 84 ng/mL at 40 min when 50 mg of intranasal ketamine was given over 25 min²¹. IV bioavailability is 93%, with oral bioavailability of 16.5%²⁵. Intranasal bioavailability is estimated to be 45%-50% from prior studies^{23, 26, and 27}. Studies from Kyle Christensen et al. have shown safety with

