Dose Finding. Escalating dosages of intranasal ketamine will be given during the study in order to find optimal analgesic dose without significant side effects. On the first study visit, after obtaining written informed consent, 10mg of intranasal ketamine will be given to make sure that the study patients are able to tolerate a small dose of NAS ketamine. On the second visit, 10 mg of IV ketamine will be given to help establish bioavailability of NAS ketamine, with patients serving as their own controls. On the third and fourth visit, higher doses of ketamine, 30 mg and 50 mg respectively, will be given, if the patients did not have severe adverse events with the smaller dosage. Licensed study personnel delegated to do so, will administer ketamine. The intranasal ketamine will be administered as follows: 1) Ensure mucosal atomization device (MAD) is primed and the appropriate dose loaded into the syringe. 2) Have patient sit in chair and clear sinuses using a tissue if needed. 3) Tilt the patient's head back. 4) Insert MAD into nostril and aim directly posterior, level with the floor of the nare, and slightly lateral. 5) Administer 0.1mL (10mg). 6) Have patient keep his head tilted back for 5 minutes, if tolerable, to ensure that the medication does not run out of nares. Make a note if medication is visibly noted to run out of nares or if patient reports feeling of medication trickling down his throat. 7) If more than 0.1mL (10mg) needs to be delivered, repeat steps 3-5 in the contralateral nare, alternating until the full dose is delivered. Ensure 30 seconds have passed before re-administration into the same nare. Patients may continue to take their usual pain medication as needed. Since most of the oral immediate release opioid medications peak between 30 to 90 minutes, ketamine will be given at least 120 minutes after the last dose of immediate release opioid medication so the reduction in pain score is not confounded with the results of immediate release opioid medications. Pain scores will be recorded on NPRS prior to and at 5, 10, 15, 30, 45, 60, 120, and 180 and 240 minutes after administration of test medication. NPRS is the most responsive tool to document pain intensity when compared to Visual Analogue Scale (VAS) and Visual Rating Scale (VRS) for measuring pain,²⁹ showing higher compliance rates, better responsiveness, ease of use, and good applicability relative to VAS/VRS³⁰. In general, improvements of pain severity</=1.5 points on NPRS could be seen as clinically irrelevant³¹⁻³⁴. Above that value, the cutoff point for "clinical relevance" depends on patients' baseline pain severity, and ranges from 2.4 to 5.3³³⁻³⁵. Higher baseline scores require larger raw changes to represent clinically important differences³⁶.

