
Concomitant Opioid medications: As the study subjects will have uncontrolled pain it is likely that they might be on opioid medications during the study. Georgia prescription monitoring database will be searched by the investigators and an opioid pill count will be done at each visit to monitor opioid intake during the study.

Pharmacokinetics. Blood samples will be drawn at 2, 30, 60 and 240 minutes. Baseline blood samples will be drawn on visits 2 through 5. The specimen requirements for lab testing are 3 ml serum or plasma in EDTA containing vacuum tubes. We will draw 6 ml of blood per sample to allow for adequate serum/plasma sample. The total blood drawn during one visit would be 24 to 30 mL. Samples will be promptly centrifuged and serum or plasma will be separated into a plastic cryovial and frozen. The plastic containers will be preservative free. All samples will be sent within 3 months to National Medical Services. The samples are valid for 7 months at -20°C, 30 days when refrigerated or stored at room temperature. Samples will be destroyed immediately after analysis. A gas chromatography with mass spectrometry (GC/MS) analysis of the samples will be done for concentrations of ketamine and its metabolite, norketamine. Plasma concentration-time curves for ketamine and norketamine will be generated for each subject and compared within subjects for the variables of route and dose, with IV administration serving as the basis for comparison.

Additional Labs: Liver function test (LFT) and urinalysis (UA) will be done on visits 1 and 5.

Patient Reported Outcomes. Patients will maintain a pain diary(Appendix I-J) for the entire study period up until the 5th and final study visit and record how often they took their usual breakthrough medication during the trial.

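### The IV reference visit has no PK sample between 2 and 30 minutes and no AUC method is stated, so a per-subject trapezoid would overstate the IV AUC and modestly understate nasal bioavailability

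*Combined protocol and SAP*

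**What the plan says.** The Pharmacokinetics paragraph under C.2 states: "Blood samples will be drawn at 2, 30, 60 and 240 minutes". Footnote 9 of the Table of Assessments applies these times to Visits 1 to 4, with windows of 5 minutes at 30 and 60 and 15 minutes at 240. Visit 2 is the IV visit. The Dose Finding paragraph gives its purpose: "10 mg of IV ketamine will be given to help establish bioavailability of NAS ketamine, with patients serving as their own controls". Concentration curves are to be generated for each subject and compared within subjects, "with IV administration serving as the basis for comparison".

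Section A2 describes IV ketamine as having "distribution half-life 10 minutes; elimination half-life 2-3 hours". It also cites a study in which the elimination half-life of IV "ketamine is reported to be 126.8(+47.4) min". For the nasal route, time to peak "was found to be 22.5(+ 9.6) min for ketamine and 120(+ 52) min for its metabolite norketamine".

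On pre-dose samples the plan says: "Baseline blood samples will be drawn on visits 2 through 5". No drug is given at Visit 5, and visits are two to seven days apart.

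AUC0-t and clearance are listed in Aim 1a under Primary Outcomes. C.12 names bioavailability as a target. It gives no AUC rule, no rule for the concentration at time zero and no tail extrapolation. Compartmental model selection is mentioned only under the PK-PD item.

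**The concern.** The IV AUC is the denominator of bioavailability, and estimating bioavailability is the stated reason for giving an IV dose. The IV curve falls fastest in the first half hour, and nothing is measured there between 2 and 30 minutes. The curve is convex, so a straight line joining those two points lies above it and the AUC comes out too large. Bioavailability is then too low, and so is any clearance computed as dose over AUC. Meanwhile a PK sample is taken at Visit 5, days after the last dose, with no purpose given.

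**Working it through.** **The plan's own figure.** At 6 mL per sample, Visit 1 has 4 draws (4 × 6 = 24 mL) and Visits 2-4 have 5 (5 × 6 = 30 mL). This reproduces the stated 24 to 30 mL. Per patient: (4 + 5 + 5 + 5 + 1) × 6 = 120 mL.

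**The gap.** (30 − 2)/10 = 2.8 distribution half-lives. The fraction of the distribution component lost inside it is 2^(−0.2) − 2^(−3) = 0.871 − 0.125 = 0.746.

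**Model.**
- IV: C(t) = A·exp(−αt) + B·exp(−βt), with α = ln 2/10 and β from half-lives of 120, 126.8 and 180 min (section A2).
- Assumptions not in the documents: bolus input, and a distribution share A/(A+B) of 50-90%, i.e. A/B from 1 to 9.
- Nasal: first-order absorption with the rate set to give tmax 22.5 min, and F = 0.45 (the plan: "Intranasal bioavailability is estimated to be 45%-50% from prior studies"). Sensitivity at 22.5 ± 9.6, i.e. 12.9 and 32.1 min.
- Each AUC0-240 from the planned times, with IV C0 back-extrapolated, is compared with the exact integral.

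**One case in full (A = 3, B = 1, elimination half-life 126.8 min; arbitrary units).** C(2) = 3.6008, C(30) = 1.2237, C(60) = 0.7672, C(240) = 0.2693. Back-extrapolated C0 = 3.6008 × (3.6008/1.2237)^(2/28) = 3.889.

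Exact AUC0-240 = 43.28 + 133.67 = 176.95.

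| Segment (min) | Exact | Linear | Log-down |
|---|---|---|---|
| 0-2 | 7.59 | 7.49 | 7.49 |
| 2-30 | 57.95 | 67.54 | 61.67 |
| 30-60 | 28.22 | 29.86 | 29.33 |
| 60-240 | 83.19 | 93.29 | 85.61 |
| Total | 176.95 | 198.18 | 184.10 |

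Linear: 198.18/176.95 = 1.120. Log-down: 184.10/176.95 = 1.040. With the linear rule the 2-30 gap contributes (67.54 − 57.95)/176.95 = +5.4 points and the 60-240 gap (93.29 − 83.19)/176.95 = +5.7 points.

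The nasal AUC in this case is off by +6.5% (linear) or −1.2% (log-down). The bioavailability ratio is therefore 1.065/1.120 = 0.95 or 0.988/1.040 = 0.95.

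**Over the whole range, planned schedule.**
- IV AUC0-240: +5% to +20% (linear), +2% to +6% (log-down).
- Estimated/true bioavailability over 0-240 min at tmax 22.5: 0.95-0.97 (linear), 0.94-0.98 (log-down).
- Over tmax 12.9-32.1 min: about 0.84-0.98.
- At tmax 12.9 min in the worked case, the highest sampled nasal concentration is about 28% below the true Cmax.

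**With one added IV sample at 12 min.**
- IV AUC0-240: +4% to +12% (linear), +1% to +4% (log-down).
- Ratio at tmax 22.5: 0.96-1.04 (linear, reversing to about +3.5% at a 90% share), 0.95-0.99 (log-down).

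**Individual fit.** A two-compartment IV curve has four parameters (A, B, α, β). Four post-dose samples leave 4 − 4 = 0 residual degrees of freedom; five leave 1.

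**Visit 5.** The shortest interval is 2 days = 2,880 min. 2,880/180 = 16 half-lives and 2,880/126.8 = 22.7. At 16 half-lives the ketamine fraction left is 2^(−16) = 1.5 × 10⁻⁵.

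**The case against.** The plan does not commit to a trapezoid. C.12 refers to compartmental model selection and to individual and group parameters. A completer supplies 4 × 4 = 16 post-dose samples, and a correctly specified joint or pooled fit need not carry trapezoid bias. This stands, and it makes the finding conditional. The plan does not commit to such a fit either, and per-subject curves with AUC0-t make a trapezoid a natural reading.

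The effect on bioavailability is also small: 2-6% at the cited tmax, in a preliminary study aiming for 10 completers, with nasal errors offsetting part of the IV error. This stands too. The offset depends on each patient's tmax, however, so it cannot be relied on.

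The proposed sample recovers only about 1 point of the ratio under log-down. That is correct, and it is why the gain is described as partial. C.3 lets the investigator increase the frequency of assessments, but it names no PK times.

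Three stronger readings are tempting:
- A reader might infer that bioavailability is 8-9% too low at tmax 22.5 min. A figure near that arises only when the estimate over 0-240 min is divided by the full F of 0.45 (for example 0.411/0.45 = 0.91). That mixes in truncation at 240 min, which an early sample cannot repair.
- A reader might infer that the Visit 5 sample adds to the bias. It never enters the IV AUC.
- A reader might infer that nothing remains to measure at Visit 5. The documents support this for ketamine on IV half-lives only. Section A2 says the nasal elimination half-life is unreported and gives none for norketamine, which is also assayed. The sample could serve as a washout check, though no such purpose is stated.

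**Conclusion.** The point holds in conditional form. The schedule leaves the IV distribution phase unsampled, and the analysis method that would determine the consequence is not stated. The direction was the same in every modelled case under the planned times: IV AUC too high, bioavailability too low. The sizes rest on a per-subject trapezoid, bolus input and a 50-90% distribution share, none of which the documents give. The IV visit is not the only source of error: the 60-240 minute gap matters about as much under the linear rule, and the nasal visits have the same early gap, which contains the cited tmax. The Visit 5 sample is a question of where a draw is best spent. This is worth changing because it touches measures listed under Primary Outcomes and costs little, but it does not invalidate the PK comparison.

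**What to change.** 1. Add a PK sample at Visit 2, 10-15 minutes after the IV dose, and drop the Visit 5 PK sample to pay for it. Total draws stay at 4 + 6 + 5 + 5 = 20, or 120 mL.
2. State in C.12 that AUC uses linear trapezoids on rising segments and logarithmic ones on falling segments, and state how C0 and the tail are handled. The rule matters: with linear trapezoids the extra IV sample can overshoot.
3. Amend footnotes 9 and 10, the Visit 5 entry in the blood-sample row, and the Pharmacokinetics paragraph (times, baseline visits, volume). Visit 2 becomes 6 × 6 = 36 mL, above the stated 24 to 30 mL.
4. Acknowledge that the 60-240 minute gap and the nasal peak remain thinly sampled.

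Cost: 6 mL more blood at Visit 2, several small text edits, and loss of whatever washout check Visit 5 offered. Footnote 4 already provides a separate line for blood draws at Visit 2, and staff already record pain and vital signs at 10 and 15 minutes.

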intranasal doses of ketamine at 10 mg, 30 mg and 50 mg ²⁸. Therefore, for study purposes 10mg, 30 mg and 50mg of intranasal ketamine will be administered. Each visit will be two to seven days apart to avoid any accumulation of study doses. Subjects will be recruited at the supportive oncology clinic, oncology clinics, the pain clinic and Acute Pain Service at Emory. Subjects may be identified and contacted via telephone with information about the study prior to their next clinic appointment in order to allow time for them to consider the study. After informed consent has been obtained, study eligibility will be confirmed (see Table of Assessments). An appointment will be made for the Phase I Unit at Winship. A family member/friend must transport the patient home following drug administration, as driving for 24 hours post drug administration is discouraged. Written informed consent will be obtained prior to performance of study procedures, either while recruiting prior to study visit one or during the first study visit, prior to beginning the study. Subjects must meet all study eligibility criteria on Visit 1 prior to study treatment. Patients will be asked to return to the Phase 1 Unit for a total of 5 study visits. All study visits to the clinic will take place within six weeks or less. A telephone call visit will occur 14 days after the last dose of medication administered to follow any ongoing adverse events that occurred during the study period. If there are no ongoing adverse events at the end of visit five, the subject's participation will end at that time. Subjects may be reconsented if withdrawn early, at the discretion of the investigator, provided all eligibility requirements are met.

Table of Assessments

Assessments	Screening	Visit One	Visit Two	Visit Three	Visit Four	Visit Five	Telephone Call
Review of Inclusion/Exclusion	X						
Informed Consent	X						
Med Hx/Demographics	X						
Hemoglobin (if none within 3 months of Visit One)		X					
Urine pregnancy test-within one week of planned Visit (women of child bearing potential)		X	X	X	X	X	
PHQ9 Depression Screening	X	X ¹					
Completion of PROMIS Questionnaire		X				X	
ECOG score		X	X	X	X	X	
ESAS		X	X	X	X	X	
MADRS ^{2,3}		X	X	X	X	X	
Height		X					
Weight		X	X	X	X	X	
IV access		X	X ⁴	X	X		
Study Medication Administration		X	X	X	X		
Vital Signs(HR ⁵ , BP, RR, Pulse Oximetry ⁶)		X ⁷	X ⁷	X ⁷	X ⁷	X ⁸	
Blood Samples (PK)		X ⁹	X ^{9,10}	X ^{9,10}	X ^{9,10}	X ¹⁰	
Hepatic Function test		X				X	

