4. ECOG and ESAS score at baseline on each visit
5. Sedation level on RASS scale prior to and at 30, 60 and 240 minutes after medication is given
6. If RASS score is between +4 to -3 then sedation/delirium assessment on CAM scale will be done prior to and at 30, 60 and 240 minutes after medication is given
7. Side effects on SERSDA scale prior to and at 30, 60 and 240 minutes after medication is given
8. An olfactory assessment will be performed pre and post study drug administration to determine if the study medication has impacted the sense of smell.
9. Rescue medication taken; if taken, was it taken at the usual interval or longer
10. Patient response to intervention if anything besides change in NPRS is reported
11. Patient and family education regarding maintaining pain diary and reviewing discharge instructions, including when to call study coordinator or report to emergency department
12. PROMIS functional scale on the first and last day of the study
13. Any change in health status during the duration of study
14. Opioid medication pill count at the beginning of each visit
15. Only for visits 1, 3, and 4: If the patient reports symptoms of a significant upper respiratory tract infection (e.g. rhinorrhea, congestion), the study visit will be canceled and re-scheduled at a later date.

16. If changes in sense of smell are noted, a study investigator will be notified, and additional olfactory assessments will be performed, with the frequency and amount of assessments at the discretion of the investigator.
17. The frequency of the assessments may be increased at the discretion of the investigator.

The study nurse will notify the attending physician if any of the following occur:

1. Baseline HR >100 or BP>160/100 or pain score </=3 on NPRS who will make the decision of whether or not to proceed with the study visit or cancel based on the inclusion/exclusion criterion
2. After the study medication is given, vital signs change more than 20% from baseline; HR<50 or >110, SBP<90 or >180, DBP<30 or >100, RR<8 or >24 or SaO₂<90; Any side effects or unexpected results
3. Sedation on RASS scale between -1 and -5 at any time
4. Positive for delirium on CAM scale at any time
5. Presence of any possible side effects from the study drug administration

Patients will be deemed eligible for discharge after the 240 minute assessment if they meet the following:

- Vital signs are within 10% of baseline values
- RASS score is between +1 and -1

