- Side effects as noted on the SERSDA scale are valued as 2 or less, or no more than 1 point greater than their baseline value. Investigator must be notified if value is greater than 2.

Should the patient not meet these criteria at the end of the 240 minute assessments, the study nurse will contact the research physician for further evaluation and assessment.

C.4 Potential Risks

Adverse effects are dose related. No serious side effects have been reported with intranasal ketamine doses of up to 50 mg.

Common side effects of ketamine: Include sedation, somnolence, sensory illusions, dissociative feelings, blurred vision, anorexia, abdominal pain ^{38, 39}, feeling of insobriety ^{40, 41}, and dream disturbances ⁴². Dose-dependent side effects include hallucinations, agitation, nightmares, dizziness, and nausea ⁴³. At higher doses, side effects may include delirium, impaired motor function, amnesia, anxiety, panic attacks, mania, insomnia, and elevated blood pressure ⁴³. Rarely, hepatic failure⁴³ has been reported in participants with

underlying liver disease prior to ketamine administration. Additionally, chronic administration of ketamine has been associated with ulcerative or hemorrhagic cystitis, which usually resolves with cessation of ketamine administration⁴³. However this was reported in ketamine abusers and dosage being used for this study are very low. Additionally, a LFT and UA will be done the day of or up to 24 hours before both visits 1 and 5 to monitor for rare side effects. If obtained as standard of care within this time frame, these will not need to be repeated for the study. Benzodiazepines and neuroleptics have been used to successfully minimize psychotomimetic effects, such as psychosis or delirium, when ketamine is used for the treatment of pain^{44, 45}.

C.5 Management of specific side effects

Side effects unique to intranasal route: Include transient change in taste, rhinorrhea and nasal passage irritation. If the patient reports that these changes to be persistent beyond the date of administration of study drug and are moderate to severe in intensity, then a formal ENT consult will be sought.

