Cardiovascular effects: Potential effects include: increases in heart rate, systemic arterial pressure, systemic vascular resistance, pulmonary artery pressure, and pulmonary vascular resistance. In the absence of autonomic control, ketamine has direct myocardial depressant effect, usually overridden by central response. If >20% variation from baseline is noted in heart rate or blood pressure, study MD will be notified. Risk assessment will be done by the MD and appropriate medications will be given as deemed necessary. Patient will be admitted to inpatient medical oncology service for 23 hours observation if at the end of study visit a >20% variation persists despite treatment; HR >120; hypertensive urgency/emergence occurs. Hypertensive urgency is defined at SBP>180 or DBP>110. In hypertensive emergency signs or symptoms of end organ damage are noted such as blurry vision, headache, and chest pain.

Central nervous system effects: Include- tremors, increased intracranial pressure, floating sensation, hallucinations (auditory and visual), delirium, vivid dreams or illusions, confusion, restlessness, disorientation, dysphoria, dizziness, and sedation. After discontinuation of ketamine, recurrent illusions (flashbacks) can occur. Ketamine can lower the seizure threshold, especially in patients on aminophylline. Benzodiazepines such as midazolam 0.5 mg to 5 mg IV or lorazepam 0.5 mg to 5 mg IV or diazepam 0.5 mg to 10 mg IV or oral, etc. may be given to mitigate CNS side effects at the discretion of the study MD. Admission for 23 hours observation to the inpatient medical oncology service will be considered if at the end of a study visit either excessive sedation is noted or RASS score between -3 and -5 or if any severe psychological manifestations exist.

Gastrointestinal system effects: Include nausea, vomiting and increased salivation (due to increased salivary and tracheobronchial mucous gland secretions). Nausea and/or vomiting will be treated with

ondansetron 4 to 8 mg IV or PO depending upon severity. Diphenhydramine 6.25 to 25mg IV may be given, if no relief from ondansetron or if ondansetron is contraindicated. For increased salivation, not well tolerated by the patient, glycopyrrolate 0.2mg IV may be given if deemed necessary by the study MD. Admit if unable to tolerate oral liquid at the end of visit.

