Appendix II: Ketamine related information (click on files A, B, and C to open the files)

A. Test **summary sheets from NMS labs** where ketamine and its metabolites will be measured.

Lab testing ketamine.xps

B. Ketamine product insert.—PDF file

**Ketamine
Hydrochloride
Injection, USP**

Rx only

SPECIAL NOTE

EMERGENCE REACTIONS HAVE OCCURRED IN APPROXIMATELY 12 PERCENT OF PATIENTS.

THE PSYCHOLOGICAL MANIFESTATIONS VARY IN SEVERITY BETWEEN PLEASANT DREAM-LIKE STATES, VIVID IMAGERY, HALLUCINATIONS, AND EMERGENCE DELIRIUM. IN SOME CASES THESE STATES HAVE BEEN ACCCOMPANIED BY CONFUSION, EXCITEMENT, AND IRRATIONAL BEHAVIOR WHICH A FEW PATIENTS RECALL AS AN UNPLEASANT EXPERIENCE. THE DURATION ORDINARILY IS NO MORE THAN A FEW HOURS; IN A FEW CASES, HOWEVER, RECURRANCES HAVE TAKEN PLACE UP TO 24 HOURS POSTOPERATIVELY. NO RESIDUAL PSYCHOLOGICAL EFFECTS ARE KNOWN TO HAVE RESULTED FROM USE OF KETAMINE.

THE INCIDENCE OF THESE EMERGENCE PHENOMENA IS LEAST IN THE ELDERLY (OVER 65 YEARS OF AGE) PATIENT. ALSO, THEY ARE LESS FREQUENT WHEN THE DRUG IS GIVEN INTRAMUSCULARLY AND THE INCIDENCE IS REDUCED AS EXPERIENCE WITH THE DRUG IS GAINED.

THE INCIDENCE OF PSYCHOLOGICAL MANIFESTATIONS DURING EMERGENCE, PARTICULARLY DREAM-LIKE OBSERVATIONS AND EMERGENCE DELIRIUM, MAY BE REDUCED BY USING LOWER RECOMMENDED DOSAGES OF KETAMINE IN CONJUNCTION WITH INTRAVENOUS DIAZEPAM DURING INDUCTION AND MAINTENANCE OF ANESTHESIA. (See DOSAGE AND ADMINISTRATION Section.) ALSO, THESE REACTIONS MAY BE REDUCED IF VERBAL, TACTILE, AND VISUAL STIMULATION OF THE PATIENT IS MINIMIZED DURING THE RECOVERY PERIOD. THIS DOES NOT PRECLUDE THE MONITORING OF VITAL SIGNS.

IN ORDER TO TERMINATE A SEVERE EMERGENCE REACTION, THE USE OF A SMALL HYPNOTIC DOSE OF A SHORT-ACTING OR ULTRA SHORT-ACTING BARBITURATE MAY BE REQUIRED.

WHEN KETAMINE IS USED ON AN OUTPATIENT BASIS, THE PATIENT SHOULD NOT BE RELEASED UNTIL RECOVERY FROM ANESTHESIA IS COMPLETE AND THEN SHOULD BE ACCCOMPANIED BY A RESPONSIBLE ADULT.

DESCRIPTION

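### Structured side-effect rating stops 4 hours after each dose and resumes days later, so delayed dream, sleep and flashback effects rest on general adverse-event reporting and are likely under-ascertained

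*Combined protocol and SAP*

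**What the plan says.** Specific Aim 2a names SERSDA as the side-effect measure and stands under the primary outcomes. C.3 item 7 schedules it: "Side effects on SERSDA scale prior to and at 30, 60 and 240 minutes after medication is given". C.3 items 5 and 6 give the same times for RASS and, where RASS allows, CAM. Footnotes 8 and 11 of the Table of Assessments apply the SERSDA and RASS times to Visits 1 to 4 and add one rating on arrival at Visit 5.

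C.3 ties leaving the unit to the last rating: "Patients will be deemed eligible for discharge after the 240 minute assessment if they meet the following". On spacing, C.2 says: "Each visit will be two to seven days apart to avoid any accumulation of study doses".

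On the harms themselves:

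- C.4 states "Dose-dependent side effects include hallucinations, agitation, nightmares, dizziness, and nausea", and also lists dream disturbances and insomnia.
- C.5 adds vivid dreams and says: "After discontinuation of ketamine, recurrent illusions (flashbacks) can occur".
- The package insert in Appendix II-B says of emergence reactions that "THE DURATION ORDINARILY IS NO MORE THAN A FEW HOURS", but that in a few cases "RECURRANCES HAVE TAKEN PLACE UP TO 24 HOURS POSTOPERATIVELY".

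Between visits, patients log pain three times a day and "record how often they took their usual breakthrough medication during the trial". No side-effect entry at home is described. C.13 item 5 collects adverse events from the first dose through Visit 5, and the Table of Assessments lists them at every visit.

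C.12 item 2.iii plans a chi-square test on whether any side effect is present and, if needed, a signed-rank test on the severity of all side effects, SERSDA among them.

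**The concern.** The structured instrument covers the four hours in the unit. Several effects that the protocol itself names could appear after that: a nightmare during the following night, or an illusion that returns the next day. When the instrument is next used, it asks about a different moment and has no item for these effects.

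Side effects are a primary outcome, and the Dose Finding paragraph looks for an analgesic dose without significant side effects. C.2 foresees offering the drug to outpatients who benefit, and C.14 names home maintenance as the next research step. For that use, what happens during the night and day after a dose is part of tolerability. If these effects are recorded less completely than those in the unit, the tolerability profile will look better than it is. A relation to dose would also be harder to see, for effects that C.4 says depend on dose.

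**Working it through.** The plan states no figure on this point, so the check is interval arithmetic followed by a comparison of sections.

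**Timing**

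Inputs: last structured rating at 240 min (C.3 items 5 to 7; footnote 11 allows ±15 min); visits 2 to 7 days apart (C.2); latest recurrence time of 24 h (Appendix II-B). Visits are taken to start at about the same clock time.

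- Last rating: 240 / 60 = 4 h after dosing.
- Next rating: 2 × 24 = 48 h at the earliest, 7 × 24 = 168 h at the latest.
- Gap: 48 − 4 = 44 h to 168 − 4 = 164 h.
- Part of the insert's 24 h without a structured rating: 24 − 4 = 20 h, and 20 / 24 = 83%.

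Since 48 h exceeds 24 h, no scheduled rating falls between 4 h and 24 h after any of the four doses. The 83% is clock time only. It is not a share of events lost.

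**Could the next rating recover the events?**

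The ten SERSDA items in Appendix I-B are fatigue, dizziness, nausea, headache, feeling of unreality, changes in hearing, changes in vision, mood change, generalized discomfort and hallucination. None concerns dreams, nightmares, sleep or flashbacks, and the form gives no recall period. MADRS has a reduced-sleep item, but C.2 uses that scale for patients on antidepressants or with PHQ-9 above 4, and the item does not ask about dreams.

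**What other routes exist?**

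| Route | Covers 4–24 h? | Prompts for these effects? | Severity scale |
|---|---|---|---|
| SERSDA, RASS, CAM | No | Hallucination, unreality, mood and delirium, at the time of rating only | Own scale |
| Home diary, as described | Yes | No; pain and breakthrough use | None for side effects |
| Adverse-event log (C.13) | Yes | No prompt list stated | CTCAE grade |
| Health-status changes, call instructions (C.3 items 11, 13) | Yes | No prompt list stated | None stated |

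Delayed effects therefore have a way into the record, but not through the named side-effect measure and not by a stated question.

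**What does the analysis do with them?**

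C.12 item 2.iii is worded broadly enough to include adverse events. It does not say which source feeds which test, what time window applies, or how an event between visits is assigned to a dose.

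**What one event weighs**

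With the planned minimum of 10 completers, one unrecorded patient-event at a dose moves the observed incidence by 1 / 10 = 10 percentage points.

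**The case against.** The strongest reply is that adverse-event capture has no gap. It runs from first dose through Visit 5, is scheduled at every visit and is graded on CTCAE. Patients and families are told when to call, changes in health status are documented, and assessments may be made more often. The documents do not say that adverse events are collected only when volunteered. All of this stands. A reader might infer that delayed harms would be missed altogether; the documents do not support that.

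Three further readings also go too far:

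- *The side-effect tests use only 30 to 240 min.* Item 2.iii speaks of any and all side effects and names SERSDA as one of them, so it is not confined to those ratings.
- *Comparison by dose is impossible.* One dose is given per visit, so a dated event can be assigned to the preceding dose. The plan just does not say that this will be done.
- *Lingering effects spoil the next pre-dose baseline.* The only timed figure for these reactions ends at 24 h, and the next baseline comes at 48 h or later. C.14 allows that ketamine might act beyond its usual duration, but there it speaks of pain scores. No text shows a side effect lasting to the next visit.

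The 24 h figure is also narrow. It comes only from the insert, concerns recurrences after surgery in a few cases, and stands beside the statement that reactions ordinarily last a few hours. C.4 and C.5 give no onset time for nightmares or flashbacks; that nightmares come after discharge is an inference from when people sleep. The diary form is only partly readable, so its content is taken from the narrative.

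What survives is a matter of completeness. General reporting without a prompt is a weaker instrument for these effects than the rating used in the unit.

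**Conclusion.** The point holds as likely under-ascertainment. Structured ratings end at 4 h and resume about 44 to 164 h later, and SERSDA neither names the delayed effects nor looks back in time. Those effects depend on general adverse-event reporting, with no stated prompt and no SERSDA severity score, and item 2.iii gives no rule for source, window or dose.

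The number of events affected cannot be computed: the documents give neither the frequency of delayed effects at these doses nor the completeness of adverse-event reporting. The insert's figure of about 12% for emergence reactions describes the drug as an anesthetic and should not be carried over. The conclusion rests on two assumptions: that some of the listed effects arise after discharge, and that a specific question finds more of them than general reporting does. It is a worthwhile, inexpensive improvement to measurement and does not show that the trial's safety oversight fails.

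**What to change.** At the first SERSDA of Visits 2 to 5 (pre-dose at Visits 2 to 4, on arrival at Visit 5):

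1. Ask each item twice: *now*, and *worst since you left after the last dose*, with date of onset for the second.
2. Add one line on nightmares or vivid dreams and on flashbacks since the last dose, on the same 0 to 4 severity scale.

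In C.12 item 2.iii, state that:

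- the *since last dose* answers, together with dated adverse events, are analysed as outcomes of the preceding dose. On the full schedule, Visit 2 covers intranasal 10 mg, Visit 3 the intravenous dose, Visit 4 intranasal 30 mg and Visit 5 intranasal 50 mg; Visit 5 always covers the last dose given;
- only the *now* score serves as the pre-dose baseline;
- each test names its data source and time window.

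The cost is a few extra questions on an existing form and one more table, with no new visit, contact or sample. The downside is recall over two to seven days, which will blur severity and onset; recalled scores should be shown separately from the timed ones. The change concerns measurement only and leaves the dosing, discharge and stopping provisions as they are.
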